Patients will be fasted for a minimum of 4 hours. No sedation will be administered for these FibroScan™ assessments. The exam time is estimated to be 10 to 20 minutes.

The thoracic perimeter of the patient will be measured and recorded. The thoracic perimeter value will determine selection of the probe as follows: >70cm M-probe, >45cm S2 probe, ≤ 45 cm S1 probe. The patient will be positioned in the dorsal decubitus position with the right arm in maximal abduction. The operator will sit on a chair on the right side of the patient facing both the patient's chest and the screen of the device. A small amount of coupling gel is applied to the right chest wall. The probe is placed on the chest wall, in the mid-axillary line, over the right lobe of the liver (identified by percussion) between the ribs, angled towards the middle of the parenchyma and away from the liver border. The probe is adjusted until a liver portion, free of large vascular structures, is identified. The probe is kept perpendicular to the skin and a firm amount of pressure is applied. When all these conditions have been met and an ideal window of liver tissue is identified on the device screen, the button on the probe is pressed, without changing the probe position. The device records and displays the validity of each measurement based on standardized criteria determined by Echosens. Repeated measurements are performed until 10 valid values are obtained (maximum of 16 attempts)

A second measurement site will then be identified that is one intercostal space superior or inferior to the initial measurement site. The TE measurement will be repeated at this second site, as described above.

After the end of the examination the gel is removed from the patient's chest wall with a soft tissue. Gel is also removed from the probe with a soft towel and it is then disinfected with a solution containing quaternary ammonia. The report is printed

August 12, 2016

and a non-identifying study ID label is applied. The report will be placed in the research binder and not in the clinical chart.

FibroScan™ is based on vibration controlled TE at 50Hz. FibroScan measures 2 parameters:

- “Liver stiffness” quantifies liver fibrosis and is measured in kPa (median of 10 subsequent valid measurements and are deemed acceptable if the ratio of interquartile range and median is <30% and success rate is >60%, meaning 10 valid measurements are obtained within 16 attempts).

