- “Controlled Attenuation Parameter (CAP)” quantifies liver steatosis and is measured in dB/m (median of 10 subsequent valid measurements).

In addition quality control data are collected:

- Invalid measurements and success rate
- Number and list of valid measurements
- Inter quartile range (IQR) (kPa or dB/m) of all valid measurements within the examination (reflects the dispersion of stiffness or CAP measurements)
- IQR/med. (%) Indicates the IQR/median ratio and should remain as low as possible to ensure reliable results (goal < 30%)

Study withdrawal/discontinuation

The participant and/or participant’s family may withdraw from the study at any time. The study investigator can withdraw the participant from the study at any time if that is felt to be in the best interest of the participant and/or their family. If a participant in the longitudinal follow up study meets an endpoint for the end of the PUSH study (liver transplantation or death) they will have met the end of this study.

Statistical and Design Considerations

Based upon interest and involvement of the subjects in PUSH, we anticipate all subjects currently available (168) will enroll. If TE becomes available at the 3 centers without TE, then up to an additional 60 subjects would be available to enroll. TE would be available from all eligible US pattern subjects.

Hypothesis 1: TE results can differentiate children with a heterogeneous or homogeneous pattern on grayscale liver US who will progress to a nodular pattern on US

Analysis:

To test whether TE, when combined with US pattern characterization can improve the prediction of progression to a nodular pattern on US, we will build two discrete survival models using logistic regression. In the first model, greyscale US consensus grade will be used to predict prediction to nodular pattern. In the second model, we will add the predictor liver stiffness measured by TE. If the second model significantly increases the area under the receiver operating characteristic curve

August 12, 2016

(AUROC) comparing to the first model, we will conclude that TE can improve the prediction of progression to a nodular pattern on US. All subjects graded as NL, HMG, or HTG at the time this ancillary study starts will be included in the analysis.

Power calculations:

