The estimated 2-4 year progression rate is ~40% in HTG subjects. Thus of the 33 available with HTG pattern, 10-13 would be predicted to progress to CIR. However, as the study is in progress, ~20% have progressed so the risk of progression may be lower. We choose to make a conservative assumption in our power calculation: 20% of HTG subjects will progress to CIR pattern, and 2% of NL or HMG subjects will progress to CIR pattern. In addition, we assume the liver stiffness measure follow a lognormal distribution with location =0 and scale parameter =0.5 (i.e. median=1, Q1=0.71, Q2=1.4). With 142 subjects (approximately 63% NLs, 23% HTGs, and 13% HMGs) we will have 80% power to detect an odds ratio of 4 for a 1 unit increase in the liver stiffness measure. (Caveat: Given that we do not have any preliminary data of TE measures in CF subjects, the results of this power calculation only give us a general guidance).

Hypothesis 2a: Valid TE measurements will be obtained in more than 90% of children with CF

Analysis:

For hypothesis 2a, we will estimate the proportion of subjects in whom a valid transient elastography measurement can be obtained. At each site, all measurements will be performed by one of the trained examiners. The results will be reported as the median of 10 valid measurements and will be accepted as valid if the ratio of the interquartile range (IQR) and median was < 30% and the success rate was > 60% (8, 9). Per Goldschmidt 2013 (9) we will define two measures of the feasibility of transient in our population: “technically possible” and “acceptable quality.” The proportion of subjects with a “technically possible” FibroScan™ is defined as the number of subjects with at least 10 FibroScan™ measurements obtained divided by the number assessed. The proportion of subjects with FibroScans™ of “acceptable quality” is defined as the number of subjects with FibroScan™s with the ratio of the interquartile range and median of the 10 measurements <30%, divided by the number assessed. The proportions and their 95% confidence intervals will be provided using the Wald method. We will do a stratified (separate) analysis by <8 years of age and >8 years of age. There will be the opportunity to compare this data to children with other liver diseases in the ChiLDReN FORCE study.

Hypothesis 2b: To determine the variability of TE measurements taken at different liver sites in the same patient

Analysis

August 12, 2016

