Variability of TE measurements at a single liver site will be quantified by the ratio of the interquartile range and the median (RIM). Absolute difference in RIM between the two liver measuring sites in the same patient will be calculated. Distribution of this absolute difference will be studied using kernel density estimation to identify whether the distribution has more than one mode (whether these are heterogeneous groups according to difference in variabilities between sites in the same patient). We will also study whether this RIM is associated with the median of the stiffness measurements in the same patient.

Hypothesis 3: TE based values will correlate with conventional biomarkers of fibrosis/liver disease severity in CF: APRI, Fib-4, platelet count and spleen size

Analysis: Graphic method will be used to explore relationship between TE based values and conventional biomarkers. Pearson or Spearman correlation will be calculated.

Exploratory analyses:

Hypothesis 4a: The combination of grayscale liver US image pattern assessment and TE values with fat content will differentiate between those individuals with dichotomous radiology grades (2HTG/2NL 2HTG/2HMG or 2HTG/2CIR) and risk of progression to cirrhosis.

Analysis:

ANOVA or Kruskal-Wallis test, whichever is appropriate, will be used to compare TE measures between the three groups.

Hypothesis 4b: Higher fat content will be associated with a lower risk of progression to cirrhosis

To test whether subjects with a high TE determination of fat content and heterogeneous pattern on US will not progress to an US pattern of cirrhosis (Hypothesis 5b), we will add the TE measure of fat content to the second model for testing hypothesis 1 (i.e. this model will include three predictors: grayscale US, liver stiffness, and fat content). The hypothesis can be tested through testing the regression coefficient for the fat content variable. A significant negative regression coefficient will support our hypothesis. All subjects graded as NL, HMG, or HTG at the time this ancillary study starts will be included in the analysis.

Hypothesis 5: Among those children with a nodular pattern on US, TE results will correlate with clinical findings of portal hypertension (splenomegaly, thrombocytopenia, variceal hemorrhage and/or ascites)

Analysis:

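### Hypothesis 2b: more than one mode in a kernel density of the between-site RIM difference is not by itself evidence of heterogeneous groups of children

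*Protocol*

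**What the plan says.** The analysis stands in the Protocol under Statistical and Design Considerations, Hypothesis 2b.

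- Measure at one site: "Variability of TE measurements at a single liver site will be quantified by the ratio of the interquartile range and the median (RIM").
- Quantity compared: "Absolute difference in RIM between the two liver measuring sites in the same patient will be calculated".
- What is done with it: "Distribution of this absolute difference will be studied using kernel density estimation to identify whether the distribution has more than one mode". A parenthesis gives the meaning of that finding: "whether these are heterogeneous groups according to difference in variabilities between sites in the same patient".

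The section on transient elastography measurements supplies the data. At each site, "Repeated measurements are performed until 10 valid values are obtained (maximum of 16 attempts"), and "The TE measurement will be repeated at this second site, as described above". The quality-control items kept for each exam include "Number and list of valid measurements".

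Under Hypothesis 2a an exam is "accepted as valid if the ratio of the interquartile range (IQR) and median was < 30"%, with a success-rate condition as well. The Protocol does not say whether Hypothesis 2b uses all exams or only those that meet this limit.

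Variability between sites is a secondary objective in the Design Synopsis. No error rate, power or sample size is given for it.

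**The concern.** The text fixes a criterion (more than one mode) and what it would mean (groups of children whose two sites differ in variability). The criterion has no reference for what chance alone produces. A kernel density of about 150 skewed, non-negative values commonly shows small bumps in its right tail. Conversely, a subgroup with noisier readings at one site may stretch that tail without adding a peak. The number of modes can therefore be high without groups, and groups can exist without a true second mode. At stake is a report of spurious subgroups of children with discordant sites, under a secondary objective. The primary aim is not affected.

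**Working it through.** The Protocol states no figure for this hypothesis, so there is none to reproduce. The check is a simulation.

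**Inputs from the Protocol.** 10 valid readings at each of 2 sites; RIM = IQR / median; D = |RIM1 - RIM2|; 166 subjects at centers with elastography (Design Synopsis table) and 90% success (Recruitment, enrollment and follow-up), so 166 x 0.90 = 149.4, about 149. The statistical section says 168 subjects, which gives 168 x 0.90 = 151.2; the difference is immaterial.

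**Assumptions.** Readings are lognormal. Set A: within-site log-SD 0.13 for every child, or varying between children but equal at both sites. Set B: log-SD 0.18, constant or varying continuously between children (spread 0.3), plus a half-normal D.

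**Step 1: true shape with no groups.** If a child's two RIM values are independent draws from the same single-peaked distribution, their difference is symmetric with one peak at zero. Averaging over children with different dispersion keeps that shape, and folding at zero gives a density that only falls. There is exactly one mode. 400,000 draws agree.

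**Step 2: why the estimate adds modes.** The rule-of-thumb bandwidth is h = 0.9 x s x n^(-1/5), with s = min(SD, IQR/1.34). Since 149^(-1/5) = 0.368, h = 0.9 x 0.368 x s = 0.33 s. Two equal Gaussian kernels separate into two peaks once they lie more than 2h apart, here 0.66 s. As a guide, gaps of that size are easily found in a sparse tail.

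**Step 3: no groups, n = 149, share of samples with more than one mode.**

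| Setting | Rule of thumb (0.9) | Wider bandwidths | Sheather-Jones |
|---|---|---|---|
| A, constant log-SD | 70% | 45%, 49% | not run |
| A, varying log-SD | 90% | 75%, 78% | not run |
| A, only RIM <30% | 50-58% | 23-35% | not run |
| B, constant log-SD | 68-70% | 40-44% | 78-98% (all B settings) |
| B, varying log-SD | 87-90% | 72-78% | as above |
| B, half-normal | 59-62% | 32-34% | as above |
| B, only RIM <30% | 43-47% | 18% | as above |

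Wider bandwidths are 1.06 s n^(-1/5) and SD x n^(-1/5) in set A, and 1.06 x SD x n^(-1/5) in set B. Reflecting the data at zero does not help (set A, rule of thumb: 73% and 91%). Ignoring bumps below 5% of the peak lowers set B to 35-53% (rule of thumb) and 7-18% (wider), but Sheather-Jones stays at 71-91%. A further run of set A-type settings gave 11-49% with that floor.

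**Step 4: real groups.**

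- 30% of children with log-SD 0.20 or 0.30 against 0.10 at one site: the true density of D still only falls (400,000 draws). More than one mode appears in 80-99% of samples with all exams.
- Same with 0.20 against 0.10, only RIM <30%: 61%, 36% and 34% under the three set A bandwidths. No groups, with log-SD varying by 0.4 on the log scale: 62%, 35% and 39%.
- Set B, rule of thumb, half of the children with 2-3 times the dispersion at one site: 84-90%, against 68-90% with no groups (constant or varying log-SD).
- With the 5% floor, a 30% group at 0.30 against 0.10: 41-95%, against 11-49% with no groups.
- Two widely separated groups (30% centered at 0.30, the rest near 0): 100% under every bandwidth.

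**Step 5: a calibrated test of one mode.** Silverman's critical-bandwidth bootstrap at nominal 5% (60 replicates) rejected in 0%, 2%, 5% and 17% of no-group samples, 7-23% with modest groups and 100% with widely separated groups. The 17% arose with varying log-SD; its rough 95% interval is 0.17 +/- 1.96 x sqrt(0.17 x 0.83 / 60), or 7% to 27%, so the level is not assured there.

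**Step 6: a within-child permutation test.** Divide each reading by its site median, pool the child's 20 values, reshuffle them into 10 and 10, recompute D, and compare the observed mean D with this reference. When dispersion was equal at both sites it rejected in 3.2% and 2.0% of samples (0-1% in a separate run). With a 30% group it rejected in 98.8% (0.20 against 0.10) and 100% (0.30 against 0.10). It also rejected in 95-100% when dispersion varied continuously and independently between sites, and in 100% when every child had the same shift (0.10 against 0.15). Neither of these last two has groups.

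**The case against.** The strongest reply is that the text only says the distribution will be studied. It sets no test and no rule for a conclusion, unlike Hypothesis 1, where a significant gain in AUROC leads to a stated conclusion. Hypothesis 2b is worded as something to determine, not as a claim to test. Bandwidth, treatment of zero and the smallest bump that counts may belong in an analysis plan that is not shown, and they drive the rates. With bandwidth 1.06 x SD, false modes in two no-group settings fell from 40% and 71% to 11% and 15% with a 5% floor, and to about 5% with a 10% floor.

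Much of this stands. A reader might infer that the Protocol decides the existence of groups by counting modes, that it will most likely report groups from noise, or that the plot cannot tell groups from none. The documents do not support these readings. No decision rule is written, the false-mode rate depends on an unstated bandwidth, and widely separated groups are found every time.

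What does not fall is the link itself. The Protocol names more than one mode as the sign of groups. Calibrating the mode count removes most false modes but leaves modest groups largely undetected (7-23%), so later detail would not make the count a good general indicator. It is also fair that the permutation test answers a different question; the fix below says so.

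**Conclusion.** The point holds in a limited form: more than one mode in this density is not, on its own, evidence of heterogeneous groups. With about 149 children and no groups, extra modes appear in about 40-90% of samples using all exams, about 25-60% using only exams with RIM below 30%, and about 11-49% with a 5% floor. Single settings fall outside these ranges: down to 32%, 18% and 7% respectively with the widest bandwidth, and up to 98% with Sheather-Jones. Groups that differ moderately in dispersion usually leave one true mode, so the count does not track them.

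Every rate depends on assumed lognormal or half-normal distributions and assumed log-SDs. The structural argument in Step 1 needs only equal, single-peaked RIM distributions at a child's two sites.

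Severity is minor. The aim is secondary and descriptive, no sample size or primary conclusion depends on it, and the individual readings are kept.

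**What to change.** 1. Keep the kernel density of the absolute RIM difference as a descriptive plot, and state that no conclusion about groups will be drawn from the number of modes alone.
2. For the secondary objective on between-site variability, compare the observed mean absolute RIM difference with the within-child permutation reference of Step 6, and report the excess over the reference with its interval.
3. State that this tests whether variability differs between a child's two sites beyond sampling noise, and that it does not test for distinct groups.
4. Require a calibrated unimodality test, such as Silverman's, before any claim of groups. Acknowledge its low power for modest groups, and check its level when dispersion varies between children.

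The cost is a change of wording and a short program. No new data are needed, because the valid readings of each exam are already listed. The downside is slightly more analysis work and a more cautious statement about groups.

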- **Cincinnati** - Cincinnati Children's Hospital Medical Center
- **Aurora** – University of Colorado SOM and Children's Hospital Colorado
- **Houston** – Baylor Medical College and Texas Children's Hospital
- **Indianapolis** – University of Indiana and Riley Hospital for Children
- **Minneapolis** – University of Minnesota
- **Seattle** – University of Washington and Seattle Children's Hospital
- **St Louis** - Washington University and St Louis Children's Hospital
- **Toronto** - The Hospital for Sick Children and University of Toronto

Fibroscan is available through the NIH at the bolded centers. Baltimore and Minneapolis and St Louis do not have Fibroscan available at this time. If it becomes available, they will participate in this study.

The CFLD NET study is supported by the ChiLDReN Data Coordinating Center (DCC) at the University of Michigan/Arbor Research and the clinical component is funded by the CF Foundation

Study Aims and Hypotheses

- Primary Objective:
- Aim 1:
 - To determine if transient elastography (TE), when combined with ultrasound (US) pattern characterization can improve the prediction of progression to a nodular pattern on US.
 - - o Hypothesis 1: TE results can differentiate children with a heterogeneous or homogeneous patterns on grayscale liver US who will progress to a nodular pattern on US
- Secondary Objectives
- Aim 2: To confirm the feasibility of obtaining TE measurements in children with CF
 - o Hypothesis 2a: Valid TE measurements will be obtained in more than 90% of children with CF
 - o Hypothesis 2b: To determine the variability of TE measurements taken at different liver sites in the same patient
- Aim 3: To prospectively assess whether TE data are associated with conventional markers of hepatic fibrosis and portal hypertension
 - o Hypothesis 3: TE based values will correlate with conventional biomarkers of fibrosis/liver disease severity in CF: APRI, Fib-4, platelet count and spleen size
- Exploratory Objectives:
- Aim 4: To determine if TE with fat content can improve assignment of grade in situations where there is a dichotomy of radiology grades (i.e. 2 HTG, 2NL)

August 12, 2016

- Hypothesis 4a: The combination of grayscale liver US image pattern assessment and TE values with fat content will differentiate between those individuals with dichotomous radiology grades (2HTG/2NL 2HTG/2HMG or 2HTG/2CIR) and risk of progression to a nodular pattern on US.

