- Hypothesis 4b: Higher fat content will be associated with a lower risk of progression to a nodular pattern on US
-
- Aim 5: To determine if TE can predict the development of portal hypertension and its complications in children and young adults with CF and a nodular pattern on US.
 - Hypothesis 5: Among those children with a nodular pattern on US, TE results will correlate with clinical findings of portal hypertension (splenomegaly, thrombocytopenia, variceal hemorrhage and/or ascites)
- Aim 6: To pilot the correlation of TE and hepatic fibrosis and fat content in children and young adults with CF who have a clinically indicated liver biopsy.
 - Hypothesis 6: TE assessment of liver stiffness and fat content will correlate with steatosis and fibrosis staging on liver biopsy in CF

Inclusion/Exclusion Criteria

Inclusion criteria:

- Participants enrolled in CFLD NET PUSH study in longitudinal follow up at centers with Fibroscan available (currently 8/11 centers)
- Entry criteria for that study were:
 - CF as determined by sweat chloride >60 meq/l
 - Pancreatic insufficiency
 - Age 3-12 years old at entry
 - For entry into the longitudinal follow up subjects were in one of two groups
 - A screening US pattern of nodular liver (CIR), heterogeneous increased echogenicity (HTG) or homogeneous increased echogenicity (HMG)
 - A screening US pattern of normal (NL) matched to a HTG subject (2 NL:1HTG) by age, center and pseudomonas status

Exclusion criteria:

- Exited from the PUSH Study
- Unable / unwilling to sign consent

Recruitment, enrollment and follow-up

- Planned minimum follow up 2 years
- Recruitment period: November 1, 2016 to October 31, 2019
- Total sample size 200 subjects assuming a 90% success

US pattern	Subjects in Study at	Potentially available
------------	----------------------	-----------------------

August 12, 2016

	centers with TE	subjects at centers currently without TE
NL	90	38
HTG	33	6
HMG	19	3
CIR	24	11

Study Procedures

The research protocol will encompass the prospective longitudinal analysis of FibroScan measurements of liver stiffness in children with CF who are enrolled in the PUSH study. Visits will occur annually for at least two years, therefore there will be a minimum of three assessments, a baseline and at least two annual follow up visits.

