At each visit the comprehensive clinical data and biosample collections will occur according to the PUSH protocol. Research US is performed every 2 years. FibroScan measurements will be done using a standardized protocol at each of these visits by a designated CFLD NET investigator with a specialized CRF completed for the Fibroscan measurements.

One or two investigators will be trained at each site to perform TE measurements to ensure consistent and standardized acquisition of complete data. Fasting will be specified for these procedures. While fasting requirements can significantly complicate pediatric-based studies, adult data suggest that fasting can affect elastography values (6, 7). We have been successful with fasting for the Doppler US evaluations in this study and have processes in place to successfully do studies in fasted individuals. Thus we will plan for a minimum of a 4 hour fast for the TE. The exam time is estimated to be 10-20 minutes. No lower limit age restrictions are incorporated in this protocol to afford an accurate assessment of feasibility in children of all ages (the youngest subject in the study is currently 5 years old). No sedation is needed for TE assessments.

Schedule of Visits

Procedure	Baseline	12 months	24 months
Informed Consent	X		
TE Measurement	X	X	X
TE CRF	X	X	X
Clinical data per PUSH	X	X	X
Biospecimens per PUSH	X	X	X
Research US per PUSH (occurs every 2 years, will vary on entry phase)	US will be performed on the ongoing schedule. TE will be timed to coincide with annual bloodwork and clinical visit.		

August 12, 2016

Data Collected

Clinical and laboratory data including laboratory values, physical examination, medical history, ultrasound, and biosamples will be collected per the PUSH protocol. Additional liver biopsy results will also be collected for patients enrolled in this proposed ancillary study.

Transient Elastography (FibroScan®) measurements

Up to 6 personnel will be trained at each site to perform FibroScan™ measurements to ensure consistent and standardized acquisition of complete data. While we will focus on one or two personnel involved in PUSH at each center, FibroScan™ will be available at ChiLDReN centers for multiple studies with more investigators trained. By allowing up to 3 investigators per site, we will reduce the likelihood of missing any measurements on eligible subjects. Training will take place at each site by a designated trainer from EchoSens.

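### Hypothesis 3 names an ordinary Pearson or Spearman correlation for data collected at three or more annual visits per child, and neither fixes the visit nor allows for clustering by child.

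*Protocol*

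**What the plan says.** Aim 3 is a secondary objective: "To prospectively assess whether TE data are associated with conventional markers of hepatic fibrosis and portal hypertension". Its hypothesis is that "TE based values will correlate with conventional biomarkers of fibrosis/liver disease severity in CF: APRI, Fib-4, platelet count and spleen size". The whole analysis text, under Statistical and Design Considerations, is two sentences: "Graphic method will be used to explore relationship between TE based values and conventional biomarkers", and "Pearson or Spearman correlation will be calculated". It gives no visit, unit of analysis, test, significance level or power.

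The data are repeated. Study Procedures says of the annual visits: "therefore there will be a minimum of three assessments, a baseline and at least two annual follow up visits". On laboratory and clinical data it says: "At each visit the comprehensive clinical data and biosample collections will occur according to the PUSH protocol". The Schedule of Visits puts TE, clinical data and biospecimens at baseline, 12 and 24 months. Imaging follows another calendar: "Research US is performed every 2 years".

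Elsewhere the same chapter does address time. Hypotheses 1 and 5 use discrete survival models, and Hypothesis 5 says that the predictor is the most recent TE value. Hypothesis 3 has no matching statement.

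**The concern.** Each child will supply at least three pairs of TE with APRI, Fib-4 and platelet count. A child with a stiff liver and low platelets at baseline is likely to look similar a year later, so the pairs are not independent. An analyst who follows the text as written has two simple options. Entering every visit as a separate pair makes p-values and intervals too small. Choosing one visit keeps the error right but leaves the other visits out of this analysis.

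At stake is how far the associations reported for four markers can be trusted, and how precisely they are estimated from data that the design already collects. The primary aim is not affected.

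**Working it through.** The protocol gives no figure for Hypothesis 3, so there is nothing to reproduce. The check asks what each way of using the visits would cost.

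**Inputs**
- Visits per child: k = 3, the stated minimum.
- Children: 166 at centers with TE (synopsis table; the statistical chapter gives 168). With the 90% success rate in the protocol, 166 × 0.90 ≈ 149 have valid TE. The number hardly affects the error inflation.
- Level: 5% two-sided. This is assumed, because the protocol states it only for Hypothesis 5.
- Within-child correlation ρ, taken as equal for TE and marker: not in the protocol, so a range is shown.
- True correlation for power: 0.2, assumed, and taken to be the same between and within children.

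**Error if visits were pooled as independent.** When TE and marker are unrelated, the variance of the coefficient is inflated by

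DE = 1 + (k − 1) × ρ(TE) × ρ(marker),

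and the actual error is 2 × [1 − Φ(1.960/√DE)]. For k = 3:

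| ρ (both) | DE | 1.960/√DE | Actual error |
|---|---|---|---|
| 0.2 | 1.08 | 1.886 | 5.9% |
| 0.3 | 1.18 | 1.804 | 7.1% |
| 0.4 | 1.32 | 1.706 | 8.8% |
| 0.5 | 1.50 | 1.600 | 11.0% |
| 0.7 | 1.98 | 1.393 | 16.4% |
| 0.8 | 2.28 | 1.298 | 19.4% |
| 0.9 | 2.62 | 1.211 | 22.6% |

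A simulation with 166 children and 4,000 runs per setting agrees for Pearson: 7.8%, 10.6%, 16.7%, 19.8% and 23.2% at ρ = 0.3, 0.5, 0.7, 0.8 and 0.9. Spearman is similar. A one-visit Pearson test stayed between 4.4% and 5.7%.

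**When the error doubles.** Reaching 10% needs DE = (1.960/1.645)² ≈ 1.42, so the product of the two correlations must be at least 0.42/(k − 1):
- k = 3: product 0.21, both about 0.46.
- k = 4: product 0.14, both about 0.37.
- k = 2: product 0.42, both about 0.65. This case matters for a marker available at only two visits.

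**Power from one visit.** With Fisher's transformation, atanh(0.2) × √(149 − 3) = 0.2027 × 12.08 = 2.45. Power is Φ(2.45 − 1.96) = Φ(0.49) ≈ 69%.

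**Power from all three visits with clustering respected.** The information relative to one visit is 3/DE. Simulated power (6,000 runs, 149 children, child-clustered robust test, null error 5% to 6%) is set beside the approximation Φ(2.45 × √(3/DE) − 1.96):

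| ρ (both) | 3/DE | Simulated | Approximation |
|---|---|---|---|
| 0.5 | 2.00 | 93% | 93% |
| 0.7 | 1.52 | 87% | 85% |
| 0.8 | 1.32 | 81% | 80% |
| 0.9 | 1.15 | 75% | 75% |

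**The case against.** The strongest reply is that the protocol commits no error. It names a coefficient and no test, level or decision rule, and it never says that visits will be pooled. A correlation at one visit answers the hypothesis validly, and the choice of visit could be settled in an analysis plan that is not at hand. Repeated TE values can still be used under Hypotheses 1 and 5.

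Much of this stands. Inflation concerns p-values and intervals, not a coefficient reported purely as a description. The two costs are also not large together: at ρ = 0.9 pooling does most harm, but one visit loses little (69% against 75%); at ρ = 0.5 one visit loses most (69% against 93%), but pooled error is 11%. Nor does three pairs per child hold for every marker. The protocol does not say how spleen size is measured, and an ultrasound measure would not be available annually.

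A reader might also infer that no use of the named method is valid with repeated data. That is wrong. A Spearman coefficient from all visits, with a bootstrap that resamples children, is valid, as are correlations of child means or at each visit.

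What remains is that the protocol does not leave the method open. It names one whose standard inference assumes independent pairs, in a design built on repeated visits, and nothing in the text stops an analyst from pooling.

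**Conclusion.** The point holds as a minor one. The named correlation is not matched to the repeated design, and the text neither fixes a visit nor accounts for clustering by child. Naive pooling of three visits would give an actual error of roughly 7% to 23% for within-child correlations of 0.3 to 0.9. One visit keeps the error at about 5% but gives up a 1.15- to 2-fold gain in information (ρ = 0.9 to 0.5).

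Two stronger readings are not supported. One is that pooling at least doubles the false-positive rate: 10% is not a lower bound, and with three visits it is reached only when both within-child correlations are about 0.46 or more, values that the protocol does not give. The other is that the protocol plans to pool: it does not say so.

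The figures rest on the assumed correlations, three complete visits and a 5% two-sided level. The power comparison also assumes a true correlation of 0.2 both between and within children; a weaker within-child association would shrink the gain. Aim 3 is secondary and largely descriptive.

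**What to change.** Replace the correlation sentence under Hypothesis 3 with wording such as:

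*Association between TE and each marker will be estimated from all visits at which both are available, by a Spearman (or Pearson) coefficient with a confidence interval from a bootstrap that resamples children; alternatively, by a linear mixed model on suitably transformed values with a random intercept for child. Visits will not be treated as independent observations.*

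The two options estimate different quantities, so one should be chosen as the main analysis before the data are seen. Restricting to visits where both values exist also covers a spleen size that is not recorded annually. Separate between-child and within-child estimates are optional; Hypothesis 3 does not require them.

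The cost is slightly more analysis work, and intervals wider than naive pooling would give. No new data are needed.
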